Assessing Acceptability, Cost, and Efficacy of STELLA-Support via Technology: Living and Learning with Advancing AD

01/31/2022

NCT04335110

Protocol Title:

Assessing Acceptability, Cost, and Efficacy of STELLA-Support via Technology: Living and Learning with Advancing AD

Objectives

STELLA (Support via TTechnology: Living and Learning with Advancing Alzheimer's disease and related dementias) is a multicomponent video-conference based intervention designed to facilitate effective management of behavioral and psychological symptoms of dementia (BPSD). In the STELLA intervention, professionals ("Guides") meet with family members ("Care Partners") caring for persons with dementia. Working together, the Care Partners and Guides identify strategies to address upsetting behaviors in the moderate to late stages of dementia. The goal of this intervention is to reduce upsetting behaviors and thus care partner burden including costs.

The specific aims of this study are:

Phase 1

1. Using quantitative and qualitative approaches, assess feasibility and participant acceptability of (a) STELLA, and (b) the assessment methods (subjective measures and unobtrusive objective monitoring).
2. Using quantitative strategies, assess the preliminary effect of STELLA on (a) the affective impact of caregiving, Care Partner cognitive function and person with dementia quality of life, and on (b) Care Partner and person with dementia objective digital behavioral biomarkers (activity, sleep and time together).
3. Test the feasibility of employing digital behavioral biomarker data, combined with qualitative Care Partner feedback, to assess mechanisms of behavior change before, during and after the STELLA intervention.

Phase 2

1. Quantify the costs of delivering the STELLA intervention.
2. Quantify the cost efficacy of STELLA in relation to BPSD frequency and CP reactivity and assess the relationship between costs, BPSD, and care partner burden.

H1: There is a relationship between BPSD and cost: More BPSD behaviors and more CP reactivity to the BPSD are associated with higher out-of-pocket and implicit costs for families living with dementia.

H2: There is a relationship between out-of-pocket and implicit costs and objective measures of burden identified in the ORCASTRAIT Living Lab continuous home assessment. Higher objective burden will correlate with higher implicit and out-of-pocket costs.

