a. Care Partners and Persons with Dementia. Up to 40 Care Partners and their 40 care-recipients with ADRD will participate in this study. The primary focus of this study is on Care Partners, however, we will gather subjective and objective data on participants with ADRD to assess the effect of the intervention on Care Partner affective responses to caregiving and quality of life for both. STELLA participants will be recruited from the existing cohort of patients, and their Care Partners, who are enrolled in the ORCASTRAIT Life Laboratory (OSLL).

There has been no pilot testing of STELLA with non-English speaking care partners, and all materials have been tested in English. Therefore, only English-speaking participants are included in STELLA.

b. Inclusion and exclusion criteria. The research team will assess eligibility of interested parties based on the criteria listed in Table 1. In the event of a screen failure, data collected during screening will be destroyed at the end of the study. The recruitment team will track the number of care partners contacted for the study, the number consented, the number of those that dropped out and the number of those that completed the entire intervention.

Table 1: Inclusion/Exclusion Criteria

Participant	Inclusion	Exclusion
Care Recipient	
 Diagnosis of ADRD, moderate to late stages Exhibits 2 or more behaviors listed on RMBPC¹⁶ that are bothersome to the Care Partner and occur 3 or more times/week at study enrollment Family member of Care Partner (this can be a relative, spouse or close kin that is considered family) 	
 Dementia not related to ADRD Unable to leave Care Partner during Partner training Early stage dementia, as defined by MoCA of about 15/30 or higher.

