Aim 2: Efficacy will be assessed by calculating changes in the subjective scores before, during and after the intervention using linear regression models and controlling for age, sex and education. Since this is an exploratory (proof-of-concept) study with a small sample size, we do not expect statistically significant findings, but pre-post change and standard deviation of the change will be used to calculate the sample sizes for the next stage, a RCT (NIH Stage II⁽³²⁾, Phase 1) study.

Objective digital behavioral biomarker data collected from the ORCASTRAIT Living Lab (e.g., daily activity (steps), total sleep time, times together) will be assessed before, during and after the intervention and compared to subjective findings. Simple Spearman correlations will be used to explore the relationship of the objective continuous sensor-derived data to the subjective data, where the continuous objective digital data is collapsed to mean values which will serve as a point estimate prior to, during and after the intervention. We will compare the shift in the distribution of each of the digital behavioral biomarkers from baseline to identify relative changes during and after the intervention. We will compare the objective and subjective findings of the dyad to identify trends that correlate with burden (**Figure 1**)⁽³³⁾.

Aim 2 Anticipated Results and Implications. We anticipate that STELLA will reduce Care Partner burden and grief and improve family quality of life. These improvements in turn will decrease

Care Partner desire to place family members in long-term care. We expect these findings will be supported by both subjective and objective data.

Aim 3: Before Session 5, subjective and objective data (**Table 4**) will be compared to pre, mid- and post-intervention data to identify trends. Qualitative data will be gathered during the focus groups. Participants will be asked what they thought was most helpful about the intervention and what they thought of the format. The objective and subjective results will be used to identify which components of STELLA were most effective and which need to be modified to improve the potency of future iterations.

Aim 3 Anticipated Results and Implications. We expect to see an improvement in the objectives and subjective data, and we expect that we will need to revise the STELLA intervention. We will use information from the focus groups and the accrued data to revise as needed.

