Other quantitative analyses may be performed if they data reveal important trends.

PHASE 2

Aim 1: We will carry out a costing of the intervention to determine implementation costs of STELLA.

[figure not shown]

Figure 1: Composite model spider plot of digital behavioral biomarkers in a dyad showing potential domains associated with the degree of caregiver burden (49). Numbers are odds of having the behavior relative to low burden. Similar comparisons can be made relative to baseline (e.g. sleep time or time alone before relative to after intervention).

Aim 1 Anticipated Results and Implications. The costing will demonstrate the actual costs of delivering the intervention. This is essential for future pragmatic trials and ultimately for widespread adoption in the US health system.

Aim 2: Assess data collected from CPs for correlations between BPSD frequency and explicit costs to measure the direct cost impact of the intervention. We then assess the relationship between BPSD frequency, CP reactivity, and out-of-pocket costs for families using linear regression models and controlling for salient covariates based on preliminary correlational analysis. We will repeat this analysis for implicit costs. We will then compare both the explicit and implicit out-of-pocket costs for participating CPs to those who do not participate.

Aim 2 Anticipated Results and Implications. We expect to see a relationship between BPSD and cost. Specifically, more BPSD behaviors and more CP reactivity to the BPSD will be associated with higher out-of-pocket and implicit costs for families living with dementia. Further, we expect to find a relationship between out-of-pocket and implicit costs and objective measures of burden identified in the ORCASTRAIT Living Lab continuous home assessment. Higher objective burden will correlate with higher implicit and out-of-pocket costs. This will provide much needed data on the intervention's cost-efficacy compared to other interventions to support people living with dementia.

6. Data and Specimens.

No genetic material or specimens will be collected in this study.

a. Sharing of Results with Subjects

Results of the RMBPC and the Pre-Treatment Survey will be shared with the Care Partner prior to the intervention. This will help the Care Partner identify behaviors they want to target in the training sessions. If the memory, depression, burden or grief scores are abnormal, the Care Partner may be

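### Phase 2 Aim 2 cannot, as described, attribute a cost difference to STELLA: the correlation has no STELLA term, and the group comparison has no stated baseline, eligibility limit or adjustment

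*Combined protocol and SAP*

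**What the plan says.** The Objectives set Phase 2 Aim 2 as quantifying STELLA's cost efficacy in relation to BPSD frequency and care partner (CP) reactivity. H1 is an association: "More BPSD behaviors and more CP reactivity to the BPSD are associated with higher out-of-pocket and implicit costs".

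The Analytic Plan (section 5, Phase 2, Aim 2) gives three analyses:

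1. A correlation: "Assess data collected from CPs for correlations between BPSD frequency and explicit costs to measure the direct cost impact of the intervention".
2. Linear regressions of out-of-pocket cost on BPSD frequency and reactivity, with covariates chosen from preliminary correlations, repeated for implicit cost.
3. A group comparison: "We will then compare both the explicit and implicit out-of-pocket costs for participating CPs to those who do not participate".

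The results are expected to inform "cost-efficacy compared to other interventions to support people living with dementia".

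Table 1 (section 4b) requires at least two behaviours "that are bothersome to the Care Partner and occur 3 or more times/week at study enrollment" and excludes "Early stage dementia, as defined by MoCA of about 15/30 or higher". It also excludes care recipients who are "Unable to leave Care Partner during Partner training", and CPs who cannot find the care recipient an activity during sessions.

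On cost data, the Phase 2 text in section 5 describes a weekly out-of-pocket item for the dyads taking part, plus an item on CP time. Table 3 lists a weekly ORCASTRAIT survey that includes cost. Implicit cost is average weekly care hours times about US$29. Table 4 places caregiving hours per week in the baseline demographics.

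For comparison, Phase 1 Aim 2 does use change over time: "Efficacy will be assessed by calculating changes in the subjective scores before, during and after the intervention". That sentence concerns subjective scores. Costs are not named.

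**The concern.** The aim asks what STELLA does to cost. The analysis credited with answering that relates BPSD to cost and, as described, does not involve STELLA exposure or timing. The one analysis that does involve STELLA compares cost levels between a group selected on BPSD and stage and a group whose eligibility is not stated. Since H1 itself links BPSD to cost, the two groups could differ in cost before anyone attends a session.

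At stake is the estimate carried forward. The Background (Phase 2) says that understanding STELLA's costs will move the program toward a pragmatic trial. A difference produced by eligibility could be read there as a saving or an added cost.

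**Working it through.** **Inputs.** From the documents: 120 ORCASTRAIT dyads (section 3), up to 40 STELLA dyads (section 4a), about US$29 per care hour (section 5). The plan states no effect size, SD, alpha or sample size for Phase 2 Aim 2, so it has no figure of its own to reproduce. Every other input below is assumed, and the point does not rest on it.

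**Step 1: what each analysis contains.**

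| Analysis | STELLA group or time term | Baseline cost | Covariates |
|---|---|---|---|
| BPSD-cost correlation | none stated | none stated | none stated |
| BPSD/reactivity-cost regressions | none stated | none stated | yes, data-chosen |
| Participants vs non-participants | group | none stated | none stated |

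For any constant k, corr(B, C + k) = corr(B, C). A STELLA effect that shifts every participant's cost equally leaves the correlation unchanged. In simulation with 40 participants and a true correlation of 0.30, shifts of 0, -0.5 and -1.0 SD gave mean correlations of 0.298, 0.298 and 0.296.

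**Step 2: level comparison with zero STELLA effect.** Assume:
- the comparators are the other 120 - 40 = 80 dyads;
- the top half or top two-thirds on BPSD are eligible, and volunteering among them is random;
- the BPSD-cost correlation r is 0.2 to 0.4;
- the correlation ρ between BPSD at enrolment and BPSD when cost is measured is 0.6 to 0.8.

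Expected cost difference = r × ρ × D, where D is the group difference in mean enrolment BPSD, in SD.

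- Half eligible (60): means +0.798 (eligible) and -0.798 (ineligible). Comparators: (20 × 0.798 - 60 × 0.798)/80 = -0.399. D = 1.197.
- Two-thirds eligible (80): means +0.545 and -1.091. Comparators: (40 × 0.545 - 40 × 1.091)/80 = -0.273. D = 0.818.
- Smallest: 0.2 × 0.6 × 0.818 = 0.098 SD. Largest: 0.4 × 0.8 × 1.197 = 0.383 SD.

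Simulation of the same set-up gave 0.096 to 0.377 SD. If all comparators are eligible, D = 0 and so is this bias. For scale, the 95% half-width of a 40 vs 80 comparison is 1.96 × √(1/40 + 1/80) = 0.38 SD. Each hour per week of pre-existing difference in care time is US$29 a week, or 29 × 52 = US$1,508 a year.

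**Step 3: direction.** The two exclusions about leaving the care recipient during sessions may remove demanding, costly dyads. In a separate model with an assumed demand factor, excluding the most demanding 0 to 30% gave differences from -0.13 to +0.62 SD. The sign was negative in 5 of 60 combinations. In all five, demand had twice the weight of BPSD and 20 to 30% were excluded. This model omits ρ and allows a stronger BPSD-cost link (0.4 + 0.3 × 0.4 = 0.52), so its range is not comparable with Step 2.

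**Step 4: pre-post change in participants alone.** Regression to the mean gives a false saving of r × (eligible mean BPSD) × (1 - ρ): from 0.2 × 0.545 × 0.2 = 0.022 to 0.4 × 0.798 × 0.4 = 0.128 SD.

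**Step 5: precision of a baseline-adjusted comparison.** Approximate half-width = 1.96 × √(1 - c²) × √(1/40 + 1/n), with c the assumed pre-post cost correlation and n the number of comparators.

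| n | c = 0.7 | c = 0.3 |
|---|---|---|
| 80 (all) | 0.27 | 0.36 |
| 40 (two-thirds eligible) | 0.31 | 0.42 |
| 20 (half eligible) | 0.38 | 0.51 |

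Full Table 1 restriction could leave fewer. With 60 eligible on BPSD and a further 10, 20 or 30% excluded, 54, 48 or 42 dyads remain, hence 14, 8 or 2 comparators.

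**The case against.** **The correlation could still inform a cost effect indirectly.** RMBPC is repeated at baseline, Venus and Earth, and cost is collected weekly. A change in BPSD multiplied by a BPSD-cost slope implies a cost change, which suits the aim's wording. This stands: a reader might infer that the correlation can say nothing about STELLA, and that goes too far. But the plan does not state this step, and the product would be a model-based inference rather than a direct measurement.

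**The comparators are guessable.** Both dyad members must be in ORCASTRAIT, so the remaining ORCASTRAIT dyads are the natural reading. This largely stands, although section 4e allows recruitment from the wider community. What remains open is whether the comparators meet Table 1.

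**Cost data may exist for everyone.** Table 3 defers to the ORCASTRAIT protocol, which is not supplied, and the dyads named in the Phase 2 text could be all who answer that survey. This stands too. A reader might infer that comparators have no cost data, or that implicit cost cannot change because hours come only from the baseline form. The documents support neither: a weekly time item is also described, and the source of the hours is simply not named.

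**Adjustment and change analysis appear elsewhere.** They do not reach this comparison. The covariates belong to the regressions, and the Phase 1 change analysis does not name costs.

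**The work is exploratory.** H1 and H2 are associations, and Phase 2 has no decision rule. This limits the harm but does not remove it, because the plan still expects cost-efficacy data. The exploratory caveat is written under Phase 1 Aim 2.

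**Conclusion.** The concern holds and should be fixed, within limits. As described, Phase 2 Aim 2 can address the H1 association but does not isolate a cost effect of STELLA. Followed literally, its only STELLA contrast can return a difference that reflects eligibility.

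A reader might infer that participants must look costlier and that a real saving would be hidden. H1 and the BPSD criterion point that way, but other exclusions could act in the opposite direction, and the documents determine neither sign nor size. The simulated values show only that, under plausible assumptions, the bias can be comparable with the sampling error of the comparison. The conclusion rests on the text: no STELLA term in the correlation, no stated baseline, eligibility limit or adjustment in the comparison, and selection on a factor that the plan itself links to cost. The harm is a misleading estimate carried forward, not a false formal claim.

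**What to change.** 1. Delete the clause saying that the correlation measures the intervention's direct cost impact. Report the correlation and regressions as the H1 association.
2. Name the comparators as ORCASTRAIT dyads not in STELLA. Where the weekly cost survey covers both groups, compare post-STELLA mean weekly cost, adjusted for pre-STELLA cost, over the same calendar windows. Report a non-randomised estimate with a confidence interval. Restrict to, or adjust for, BPSD and stage only where those data already exist, as a sensitivity analysis.
3. Reconcile the Phase 2 text on whose costs are collected with the weekly survey in Table 3, so that both groups use the same cost item. Name a repeated source of care hours for implicit cost.
4. If comparators lack baseline cost, report the group difference and the participants' pre-post change as descriptive only, noting selection and regression to the mean.
5. In either case call the result a change or difference in family cost. Draw no cost-efficacy conclusion unless it is joined to delivery cost (Phase 2 Aim 1) and to the BPSD and reactivity outcomes.

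**Cost.** Items 1, 4 and 5 are wording. Items 2 and 3 need a small amount of analysis work and a common cost item, which may involve the parent study's separate IRB protocol. Intervals may widen if dyads without pre-STELLA cost drop out, and clearly widen under eligibility restriction, which is why that is a sensitivity analysis. Bias from who volunteers remains.

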ZBI ³³	
CESD-10 ³⁴	
MMCGI-SF ³⁵	
Placement plan scale ³⁷	
QoL-AD	
STELLA contact	STELLA care partner contact post intervention
STELLA Experience Survey	16-item + comments on satisfaction, privacy, ease of use
Earth Assessment	
RMBPC ²³	
 • See Baseline for descriptions • Baseline: 
 + STELLA contact survey -Experience Survey
ZBI ³³	
CESD-10 ³⁴	
MMCGI-SF ³⁵	
Placement plan scale ³⁷	

QoL-AD	-Demographic survey
STELLA contact	

Phase 2

Aim 1. Quantify the costs of delivering the STELLA intervention. This will measure the direct costs of delivering the intervention (wage multiplied by time of all personnel supporting the intervention) as well costs of technology and equipment, and any in-kind donations of equipment or time to support the intervention.

Aim 2. Quantify the cost efficacy of STELLA in relation to BPSD frequency and CP reactivity and assess the relationship between costs, BPSD, and care partner burden.

Out-of-pocket costs for participating dyads will be collected using an addition to the weekly online ORCASTRAIT survey. CPs will be queried about personal funds spent on health care services, co-pays, medications, or equipment. CP time dedicated to these care-related activities will also be collected. Implicit costs for families will be calculated by multiplying the average weekly hours of care provided by the CP by the average hourly wage of paid caregivers in Portland, Oregon (approx. \$29).

Analytic Plan.

Phase 1

Aim 1: Feasibility will be assessed by calculating the proportion of enrolled Care Partners who completed the full intervention. Reasons for drop-out and discontinuation will be investigated carefully. Focus group transcriptions will be analyzed for themes of acceptability using narrative analysis.⁽²⁵⁾

Aim 1 Anticipated Results and Implication. We anticipate that the Care Partner will find the STELLA intervention feasible and acceptable. This will provide foundational information for future proposals.

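### Phase 2 Aim 2 sets out to quantify STELLA's cost efficacy, but no analysis step sets the delivery cost against the change in BPSD after STELLA

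*Combined protocol and SAP*

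**What the plan says.** The Objectives give Phase 2 two aims: to cost the delivery of STELLA, and to "Quantify the cost efficacy of STELLA in relation to BPSD frequency and CP reactivity" while also relating costs, BPSD and burden to each other. The two hypotheses under Phase 2, H1 and H2, are both associations with family costs.

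The Phase 2 measures in Section 5 describe two separate kinds of cost:

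- Delivery cost (Aim 1): staff wage times time, plus technology, equipment and in-kind contributions.
- Family cost (Aim 2): "Out-of-pocket costs for participating dyads will be collected using an addition to the weekly online ORCASTRAIT survey", and an implicit cost obtained by "multiplying the average weekly hours of care provided by the CP by the average hourly wage of paid caregivers in Portland, Oregon", about $29.

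The Analytic Plan for Aim 1 is one sentence: "We will carry out a costing of the intervention to determine implementation costs of STELLA". For Aim 2 it assesses "correlations between BPSD frequency and explicit costs to measure the direct cost impact of the intervention", then the "relationship between BPSD frequency, CP reactivity, and out-of-pocket costs for families using linear regression models", then repeats the regression for implicit costs, and finally compares family costs of participants and non-participants. The Aim 2 implications paragraph says that this will provide data on "cost-efficacy compared to other interventions to support people living with dementia".

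**The concern.** A statement about cost efficacy needs what the intervention cost and what it achieved, reported together. Here the two are produced in different parts of the plan and never meet. A relation between symptoms and family spending stands in their place, and the plan labels it as the cost impact of the intervention.

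The Background explains why this matters: it describes payor approval as starting from an intervention's cost and its cost-efficacy relative to alternatives. Followed exactly, the plan delivers the first of these. It would then rest any conclusion on the second on an analysis that cannot support it.

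**Working it through.** The plan states no cost-effectiveness figure, sample-size derivation or power, so there is no number to reproduce. The check sets each planned step against what the aim requires.

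| Planned step | Cost used | Change in BPSD after STELLA used? | Contrast involving STELLA? |
|---|---|---|---|
| Phase 2 Aim 1: costing | Delivery | No | No |
| Phase 2 Aim 2, step 1: correlation | Explicit, from Care Partner data | No, BPSD frequency only | No |
| Phase 2 Aim 2, step 2: regressions | Out-of-pocket, then implicit | No, frequency and reactivity only | No |
| Phase 2 Aim 2, step 3: participants against non-participants | Family | No | Yes, but costs only |
| Phase 1 Aim 2: change in subjective scores | None | Yes, the RMBPC is among the measures | Before, during and after, single arm |

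**Delivery cost and effect.** Delivery cost appears only in the first row and RMBPC change only in the last. No row contains both.

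**Meaning of the step 1 correlation.** The explicit costs come from data collected from Care Partners, so they are family costs. If families facing more symptoms spend more, the correlation is present whether or not STELLA alters symptoms or spending. It is evidence on H1, and it does not isolate an effect of the intervention.

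**Comparator.** The only one is non-participation. Where those Care Partners come from is not stated. The remaining dyads of the 120 being enrolled in the parent study are a plausible source, but that is an assumption. No other intervention, external benchmark or common outcome scale is named.

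**Are the inputs planned?** Delivery cost is an Aim 1 output. Table 4 lists the RMBPC in the Mercury, Venus and Earth surveys, and Table 3 places Earth at 6 and 12 months after the intervention. Out-of-pocket cost is weekly, but the documents do not say whether the added cost questions start before Session 1. Care hours per week are listed under the baseline demographics, which Venus and Earth drop, so follow-up hours appear to depend on the parent study's weekly survey.

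**Precision illustration (assumed values).** For a mean change in n independent dyads, in SD units of change, the 95% half-width is t(0.975, n−1)/√n.

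- n = 40, the stated maximum: 2.023/6.325 = 0.32 SD.
- n = 30, an assumed number of completers: 2.045/5.477 = 0.37 SD.

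An observed mean change below about 0.32 SD would therefore have an interval that includes zero even at full enrolment, and a cost per unit of change would then be unbounded. Sessions 5 to 8 are held in groups of two to four. Full enrolment thus gives between 40/4 = 10 and 40/2 = 20 groups, and positive correlation within groups would widen the interval further.

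**The case against.** The strongest reply is that the study calls itself exploratory, never defines cost efficacy as a ratio, and states only associational hypotheses for Phase 2, to which the regressions correspond. Delivery cost and RMBPC change are both planned outputs, and anyone could put them side by side. The phrase about other interventions sits in an implications paragraph and can be read as supplying data for later use. The plan also allows further analyses if the data show trends.

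Much of this stands. A reader might infer that the protocol commits to a head-to-head comparison with other interventions, but no aim, hypothesis or analytic step does so; the phrase is loose wording. A reader might also infer that the study cannot produce the missing quantity at all; its two main components are planned. A cost-per-unit ratio is not required by the documents, and it would be fragile. A one-off delivery cost cannot be netted against a weekly family cost without a time horizon. Uncontrolled RMBPC change is open to regression to the mean, because Table 1 requires at least two bothersome behaviours occurring three or more times a week at entry.

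The reply does not remove the mismatch. Exploratory status excuses a lack of significance; it does not excuse leaving a named aim without an analysis. An unspecified allowance for further work is not a step, and the correlation is mislabelled on any reading.

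**Conclusion.** The concern holds as a mismatch between an aim and its analysis, and should be corrected. Aim 2 names cost efficacy in relation to BPSD, and no listed step sets delivery cost against RMBPC change. The association with family cost cannot take its place.

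The missing estimate has no size of error attached. The half-width of 0.32 SD is illustrative: it assumes all 40 dyads contribute and are independent, and the documents give no effect size or SD. It would be tempting to quote a fold-range for cost per unit of improvement, but that needs an assumed effect the documents do not supply, so none is given here. The conclusion rests on reading explicit costs as family costs, which follows from their stated source.

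**What to change.** **1. Add a cost-consequence table to Phase 2 Aim 2.**

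- Show mean delivery cost per Care Partner from Aim 1 beside mean change in RMBPC frequency and in reactivity, from Mercury to Venus and to each Earth survey (6 and 12 months).
- Give 95% intervals that allow for the small STELLA groups, noting that 10 to 20 groups make any such method approximate.
- Label the table exploratory, single-arm and open to regression to the mean.
- Show change in family cost as a separate row, only where cost data from before Session 1 exist, and do not net it into a ratio.
- Treat any cost per unit of change as secondary, and omit it if the interval for change includes zero.

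**2. Reword two sentences in the Phase 2 Analytic Plan.** Describe the correlation of BPSD with cost as an association between symptoms and family cost, not as the direct cost impact of the intervention. Replace the phrase on cost-efficacy relative to other interventions with wording such as: an input to a future controlled comparison with other interventions.

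The cost is one table, its intervals and two edits. The delivery-cost and RMBPC rows need no data beyond those planned; the family-cost row depends on when the added cost questions begin. The downside is a weaker stated claim and intervals that are visibly wide.
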